Protocol Authors:

Vendor:

4.0**Abstract****Title:**

Real World Study of the Effectiveness of Paritaprevir/r – Ombitasvir, + Dasabuvir without Ribavirin in Patients with chronic HCV Gt1b infection and Compensated Liver Cirrhosis in the Russian Federation- An Observational, Multi-Center Study

Rationale and Background:

According to the recently published results of TURQUOISE III, Gt1b patients with cirrhosis can be successfully treated with 3D regimen without ribavirin [6]. In this study treatment-naïve and peginterferon/ribavirin treatment-experienced patients received 12 weeks of therapy with ombitasvir/paritaprevir/ritonavir (25/150/100 mg once daily) and dasabuvir (250 mg twice daily) without ribavirin. All 60 patients enrolled in the study completed treatment, and SVR12 was achieved in 100% (95% CI, 94.0 – 100%) of patients. This treatment regime was well tolerated, suggesting a 12-week ribavirin-free regimen is appropriate in this population. The Russian label of AbbVie 3D regimen has been recently changed according to the TURQUOISE III results. This study is designed to assess the real world effectiveness and safety of 3D regimen without RBV in Gt1b patients with compensated cirrhosis in Russia.

Research Question and Objectives:**Primary objective:**

To describe the effectiveness of the interferon-free 3DAA ABBVIE REGIMEN without RBV in patients with chronic HCV Gt1b infection and compensated liver cirrhosis as evidenced by SVR at 12 weeks after the end of treatment in routine clinical practice.

Secondary objectives:

- To assess the end-of-treatment (EoT) response rate
- To assess the rate of relapse (timeframe for assessing relapse - between EoT and SVR 12)
- To describe the baseline characteristics of patients with HCV GT1b and compensated liver cirrhosis treated with AbbVie 3D regimen.
- To collect information on co-morbidities and concomitant medications in cirrhotic patients in the Russian population
- To describe the tolerability of the AbbVie 3D regimen

Study Design:

This is a prospective, multi-center observational study in patients receiving the interferon-free ABBVIE REGIMEN.

The prescription of a treatment regimen is at the discretion of the physician in accordance with local clinical practice and label, is made independently from this observational study and precedes the decision to offer a patient the opportunity to participate in this study.

Target population:

ABBVIE REGIMEN will be prescribed by physicians according to the routine clinical practice. Patient can be included in the study if he/she will satisfy the following criteria:

Age \geq 18

Treatment-naïve or IFN/RBV-experienced adult male or female patients with confirmed CHC Gt1b and compensated liver cirrhosis, receiving therapy with the interferon-free ABBVIE 3D REGIMEN initiated not earlier than 2 weeks before the enrollment or the initiation is planned not later than 2 weeks after the day of enrollment in accordance to standard of care and in line with the current local label.

Patients must voluntarily sign and the Authorization (Consent) for Use/Disclosure of Data form prior to inclusion into the study.

Patient must not be participating or intending to participate in a concurrent interventional therapeutic trial.

Variables:

Primary Variable

- The percentage of patients achieving SVR12 (undetectable viral load at 12 week) after the last actual dose of the ABBVIE 3D REGIMEN

Secondary Variables

- Baseline characteristics of patients with HCV Gt1b and compensated liver cirrhosis treated with ABBVIE 3D REGIMEN
- Co-morbidities and concomitant medication
- Serious adverse events and non-serious AEs

Data Sources:

Source documents are defined as original documents. The investigator will document patient data in his/her own patient files which will serve as source data for the study.

Study Size:

60 patients will be included in this descriptive study without any prior sample size calculation. Convenient sampling methods will be used for patients who attended routine outpatient visits, fulfilled the inclusion/exclusion criteria and had signed a patient authorization form to use and disclose personal health information.

Data Analysis:

The core population (CP) is defined as all patients of the target population (TP) (definition see above), who have started the treatment combination recommended in the current local label for their disease characteristics. Patients not receiving the treatment recommended in the local label will be summarized in the non-core population (NCP). In addition, the core population with sufficient follow-up data (CPSFU) is defined as all CP patients, who have (i) evaluable HCV RNA data ≥ 84 days after the last actual dose of the ABBVIE REGIMEN or (ii) a HCV RNA value ≥ 50 IU/mL at the last measurement or (iii) had HCV RNA < 50 IU/mL at the last measurement, but no HCV RNA measurement ≥ 84 days after the last actual dose of the ABBVIE REGIMEN due to reasons related to safety (e.g. dropped out due to adverse event) or incomplete efficacy information (e.g. virologic failure such as relapse is reported in the electronic case report form (eCRF) but date and value of the corresponding HCV RNA test is missing). The safety population (SP) is defined as all patients who received at least one dose of the ABBVIE REGIMEN.

Descriptive and exploratory statistical methods will be used to analyze the data of the study. All baseline and disease characteristics will be summarized for the CP stratified by the CP analysis groups, which are relevant for scheduled treatment and duration (12 weeks). In addition, baseline summaries will be repeated for the SP and TP without stratification into subgroups. Further details of analysis populations and the CP analysis groups will be specified in the statistical analysis plan (SAP).

The primary effectiveness analysis will be performed for CP patients, stratified by the CP analysis groups. Response rates (i.e. SVR12 rate, end of treatment [EoT] response rate, relapse rate,) will be determined for the various CP analysis groups. The relapse rates will be estimated in patients of the CP analysis groups with EoT response and sufficient HCV RNA measurements post treatment. The relapse rates will be estimated in all patients of the CP analysis groups, who have undetectable HCV RNA measurement at EoT visit. For all rates specified above 95%-confidence intervals (CIs) will be determined using the Clopper-Pearson method.

Milestones:

Start of Data Collection: 10-Mar-2017

End of Data Collection: 10-Dec-2017

Final Report of Study Results: 30-Mar-2018

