No data will be imputed for any effectiveness or safety analyses except for the analyses of the HCV RNA endpoints. When there is no HCV RNA value in a visit time window post-baseline, but prior to EoT, the closest values before and after the window, regardless of the value chosen for the subsequent and preceding window, will be used for the flanking imputation described below. If a patient has a missing HCV RNA value at a post-Visit 1

visit prior to EoT but has undetectable HCV RNA (with LLoD \leq 50 IU/mL) or unquantifiable, but detectable HCV RNA levels (with LLoQ \leq 50 IU/mL) at both the preceding and succeeding measurements, the HCV RNA level will be considered undetectable or unquantifiable, respectively, at this visit for this patient. In addition, if a patient has an unquantifiable HCV RNA level at the preceding measurement and an undetectable HCV RNA level at the succeeding measurement, or vice versa, the HCV RNA level will be imputed as unquantifiable at this visit for this patient. For virological response at EoT a corresponding backward imputation approach will be applied. This means if HCV RNA is missing at EoT, then unquantifiable or undetectable will be assumed for EoT, if the succeeding HCV RNA value is undetectable or unquantifiable. For SVR12 the single last available HCV RNA measurement \geq 84 days post-treatment will be used. Subsequent to this flanking and backward imputation, if the HCV RNA value remains missing at a specific time point, then the patients will be considered as virological failure at this time point (i.e. not undetectable or unquantifiable).

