9.13.5 Secondary Effectiveness Endpoints

The secondary effectiveness endpoints are:

- The percentage of patients with virological response (HCV RNA <50 IU/mL) at EoT
- The percentage of patients with relapse (defined as HCV RNA <50 IU/mL at EoT followed by HCV RNA ≥ 50 IU/mL)
- The percentage of patients with relapse (defined as at least one documented HCV RNA <50 IU/mL followed by HCV RNA ≥ 50 IU/mL during treatment).

- The number and percentage of patients meeting each and any of the following SVR12 non-response categories:
 - Relapse (defined as HCV RNA <50 IU/mL at EoT or at the last on-treatment HCV RNA measurement followed by HCV RNA ≥ 50 IU/mL post-treatment)
 - Missing SVR12 data and/or none of the above criteria

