9.13.6 Statistical Methods for Analysis of Effectiveness Variables

The simple percentage of patients achieving SVR12 will be calculated and an exact two-sided 95% confidence interval (CI) of the percentage will be computed based on the Clopper-Pearson method.

Corresponding methods will be used for other response rates (EoT response rate, relapse rate). The relapse rates will be estimated in patients of the CP analysis groups with EoT response and sufficient HCV RNA measurements post-treatment.

These analyses will be of exploratory nature, data driven, and will be repeatedly performed for various CP Analysis Groups, since not each covariate might be predictive in each patient group. Furthermore, the fact that treatment regimens will differ in the various patient groups has to be taken into account, when selecting the patient groups for each MLR analysis. Backward selection procedures will be applied to generate the final MLR models which consider only covariates in the selection procedure with a p-value <0.25 in the corresponding univariate logistic regression analysis. A p-value <0.05 will be used for the covariates to stay in the model in a backward elimination step. Logistic regression methods will also be used to investigate the impact of treatment adherence on SVR12.

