Table 1.13.3 Concurrent Medications for CHC (treatment-experienced groups)
Table 1.13.4 Concurrent Medications for CHC (Child Pugh score groups)

for the target and safety populations

Table 1.13.5 Concurrent Medications for CHC
Table 1.13.6 Concurrent Medications for CHC

P16-253 (CITRIN) _ STATISTICAL ANALYSIS PLAN _ FINAL 2.0 _ 16 Mar 2018
Effectiveness Analyses (TP)

 AbbVie Ltd
 P16-253

Table 2.1.1.1 Percentage for effectiveness endpoints

The target population (TP)

Page X of X

| Parameter Statistics | Total (N=XX) |
|---|------------------------------|
| | n (%) |
| | [95% CI] |
| SVR12 achieving (single last HCV RNA value <50 IU/mL 12 weeks after the last actual dose of the ABBVIE REGIMEN) | XX (XX.X) [XX.XX - XX.XX] |
| SVR12 non-response | XX (XX.X) [XX.XX - XX.XX] |
| Patients with breakthrough (at least one documented HCV RNA value <50 IU/mL followed by HCV RNA ≥50 IU/mL during treatment) | XX (XX.X) [XX.XX - XX.XX] |
| Failure to suppress (each measured on-treatment HCV RNA value ≥50 IU/mL) | XX (XX.X) [XX.XX - XX.XX] |
| Patients with relapse (HCV RNA value <50 IU/mL at EoT or at the last on-treatment HCV RNA measurement followed by HCV RNA ≥50 IU/mL post-treatment) | XX (XX.X) [XX.XX - XX.XX] |
| Patients with premature study drug discontinuation with no on-treatment virological failure (breakthrough or failure to suppress) | XX (XX.X) [XX.XX - XX.XX] |
| Patients with missing SVR12 data | XX (XX.X) [XX.XX - XX.XX] |
| Patients with virological response (HCV RNA <50 IU/mL) at EoT | XX (XX.X) [XX.XX - XX.XX] |

N: the number of subjects in the target population. n: number of subjects within a specific category. Percentages are calculated as 100 x (n/N).
 EoT: end of treatment. SVR12: sustained virological response at 12 weeks after EoT. 95% CI: 95% confidence interval (the Clopper-Pearson method).

Program code, date, time

Data extracted: DD.MM.YYYY

P16-253 (CITRIN) _ STATISTICAL ANALYSIS PLAN _ FINAL 2.0 _ 16 Mar 2018

 AbbVie Ltd
 P16-253

Table 2.1.2.1 Percentage for effectiveness endpoints without patients with missing SVR12 results
 The target population (TP)
 Page X of X

| Parameter Statistics | Total (N=XX) n (%) [95% CI] |
|---|--------------------------------------|
| SVR12 achieving (single last HCV RNA value <50 IU/mL 12 weeks after the last actual dose of the ABBVIE REGIMEN) | XX (XX.X) [XX.XX - XX.XX] |
| SVR12 non-response | XX (XX.X) [XX.XX - XX.XX] |

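### The relapse rate has three different denominators across the protocol abstract, protocol 9.13.6 and the SAP tables, and the handling of end-of-treatment responders with no later HCV RNA test is not stated

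*Protocol*

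**What the plan says.** Two consecutive sentences in the protocol abstract (4.0, Data Analysis) set the population for the relapse rate. The first reads "The relapse rates will be estimated in patients of the CP analysis groups with EoT response and sufficient HCV RNA measurements post treatment". The second reads "The relapse rates will be estimated in all patients of the CP analysis groups, who have undetectable HCV RNA measurement at EoT visit". Neither is labelled as primary or as a sensitivity analysis, and the sentence after them applies Clopper-Pearson intervals to every rate listed.

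Protocol 9.13.6 carries only the first rule, for patients "with EoT response and sufficient HCV RNA measurements post-treatment".

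Protocol 9.13.5 defines the relapse category of SVR12 non-response as "Relapse (defined as HCV RNA <50 IU/mL at EoT or at the last on-treatment HCV RNA measurement followed by HCV RNA" of 50 IU/mL or more after treatment. The same list has a separate category, "Missing SVR12 data and/or none of the above criteria". Protocol 9.13.1 says that if an HCV RNA value is still missing after imputation, "then the patients will be considered as virological failure at this time point".

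In the SAP, the shell for Table 2.1.1.1 (Section 18) has a row for patients with relapse. Its footnote defines N as the number of subjects in the target population and continues "Percentages are calculated as 100 x (n/N"). Tables 2.2.1.1 (core population) and 2.3.1.1 (core population with sufficient follow-up, CPSFU) are built the same way. SAP Section 15 states full consistency with the protocol.

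**The concern.** The two abstract rules differ in two respects. The first needs a post-treatment HCV RNA result and the second does not. The first uses EoT response, which 9.13.5 sets at below 50 IU/mL, while the second uses undetectable HCV RNA, which on its face leaves out a responder with a detected value under 50 IU/mL. The SAP tables follow neither rule: their N also includes patients who had no EoT response and so were not at risk of relapse after EoT.

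Relapse between EoT and SVR12 is a named secondary objective. HCV RNA testing is at the physician's discretion (9.13.1), and 9.15 expects missing follow-up HCV RNA, so untested responders are foreseeable. As the documents stand, a reader cannot tell which relapse rate will be reported or how those patients enter it.

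**Working it through.** **No figure to reproduce.** Neither document states an expected relapse rate. As a check of the interval calculation only, the Clopper-Pearson lower limit for 60/60 is 0.025^(1/60) = 94.04%. This agrees with the 94.0-100% that the protocol cites for the earlier 60-patient study.

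**Inputs.** The planned size is 60 (protocol 9.11). Let N be the analysis population, E the EoT responders, m those with no post-treatment HCV RNA, and r the documented relapses. The documents give none of E, m or r. I assume E = N = 60, m = 3, 6 or 12 (5%, 10%, 20%) and r = 0 to 3. I also assume that every EoT responder is undetectable, so that only the follow-up requirement separates the two abstract rules.

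**Formulas.**
- Rule A (first abstract sentence and 9.13.6): r/(E - m)
- Rule B (second abstract sentence), relapse requiring a measured value: r/E
- Rule B with the 9.13.1 missing-equals-failure rule applied to relapse: (r + m)/E
- SAP shell: r/N

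**Results for r = 2, with exact 95% intervals.**

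| m | Rule A | Rule B, measured relapse | Rule B, missing = failure |
|---|---|---|---|
| 3 | 2/57 = 3.51% (0.4-12.1) | 2/60 = 3.33% (0.4-11.5) | 5/60 = 8.33% (2.8-18.4) |
| 6 | 2/54 = 3.70% (0.5-12.7) | 2/60 = 3.33% (0.4-11.5) | 8/60 = 13.33% (5.9-24.6) |
| 12 | 2/48 = 4.17% (0.5-14.3) | 2/60 = 3.33% (0.4-11.5) | 14/60 = 23.33% (13.4-36.0) |

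**Relative size.** With measured relapse, B = A x (1 - m/E), so B is lower than A by exactly the untested share: 5%, 10% or 20%.

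**Absolute size.** The smallest gap is r = 1, m = 3: 1/57 - 1/60 = 1.75% - 1.67%, about 0.1 points. The largest is r = 3, m = 12: 3/48 - 3/60 = 6.25% - 5.00% = 1.25 points. With r = 0 both rates are 0%, and only the upper limit differs: 6.3%, 6.6% and 7.4% under A for m = 3, 6 and 12, against 6.0% under B.

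**SAP denominator.** When some patients are not EoT responders, r/N falls below both rules. With N = 60, E = 58, m = 6 and r = 2:
- A = 2/52 = 3.85% (0.5-13.2)
- B = 2/58 = 3.45% (0.4-11.9)
- SAP = 2/60 = 3.33% (0.4-11.5)

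The SAP figure is lower than A by 1 - 52/60 = 13.3% in relative terms.

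**The case against.** **Direction.** A reader might infer that the second abstract rule counts untested responders as relapse-free, so that the relapse rate is biased downward. The documents do not say this. It follows from the 9.13.5 definition, which needs a measured value and places missing SVR12 data in a separate category. That is the better reading, but the 9.13.1 rule, if applied to relapse, moves the rate up. The different EoT criterion also matters. If d responders have a detected value below 50 IU/mL and none of them relapses, B becomes r/(E - d), which is below A only when d is smaller than m. The undetectable wording may simply be loose: protocol 9.9.1 calls SVR12 undetectable viral load, and 9.13.4 defines it as below 50 IU/mL.

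**A slip in the abstract.** The methods section has one rule, so the conflict could be called editorial. A reader might also infer that deleting the abstract sentence would change the reported rate. It would not, because the SAP shells set the reported denominator. This stands, and it is why the correction has to reach the SAP.

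**Partial cover in the SAP.** SAP Section 9 repeats the frequency tables without patients in the missing-SVR12 category, and the CPSFU leaves out responders lost for reasons unrelated to safety or effectiveness. Both reduce the dilution from untested patients. Neither is restricted to EoT responders, and the repeat depends on SVR12 data rather than on any post-treatment result.

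**Size.** The gap is small beside the uncertainty. With two relapses, the rule A intervals above are 11.7 to 13.8 points wide. The endpoint is secondary and descriptive. This stands.

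**Conclusion.** The inconsistency is real. The abstract gives two incompatible denominators for one rate, 9.13.6 keeps one of them, and the SAP uses a third while claiming full consistency with the protocol. Under the measured-value definition in 9.13.5, any denominator that keeps untested EoT responders dilutes the rate, and the SAP's N adds EoT non-responders to that. Relative to the evaluable denominator, the second abstract rule dilutes by the untested share: 5-20% on my assumptions, or about 0.1 to 1.3 percentage points with 1-3 relapses among 60 EoT responders. With no relapses only the upper limit changes.

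A firm claim of downward bias goes too far, because applying the missing-equals-failure rule to relapse would give 8.3% to 23.3% in the two-relapse example, against 3.5% to 4.2% for the evaluable rate. What is established is that the rate and the direction of any distortion depend on a choice the plan does not make. The primary endpoint, SVR12, is unaffected.

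**What to change.** 1. In protocol 4.0, delete the second relapse sentence, or label it a sensitivity analysis with an explicit rule for EoT responders who have no post-treatment test.
2. In SAP Tables 2.1.1.1, 2.2.1.1 and 2.3.1.1, give the relapse row and its Clopper-Pearson interval the 9.13.6 denominator: HCV RNA below 50 IU/mL at EoT with a post-treatment HCV RNA result. State this in the footnote, since the plan does not define what counts as sufficient measurements for relapse.
3. Count relapses only among patients in that denominator. The non-response category in 9.13.5 also admits patients who qualify by their last on-treatment value; that category can be kept as a separate row.
4. Report the number of EoT responders excluded for lack of a post-treatment sample.

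The cost is one deleted or relabelled sentence, one table footnote and one extra count. The reported rate becomes slightly less favourable and its interval slightly wider. With two relapses and six of 60 EoT responders untested, it moves from 3.3% (0.4-11.5) to 3.7% (0.5-12.7).

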6.0 Milestones

Major study milestones and their planned dates are as follows:

Start of Data Collection:	10-Mar-2017
End of Data Collection:	10-Dec-2017
Final Report of Study Results:	30-Mar-2018

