9.0 Research Methods

9.1 Study Design

This is a prospective, multi-center observational study in patients receiving the interferon-free ABBVIE REGIMEN without RBV. The prescription of a treatment regimen is at the discretion of the physician in accordance with local clinical practice and label, is made independently from this observational study and precedes the decision to offer a patient the opportunity to participate in this study.

Adult patients chronically infected with HCV and compensated liver cirrhosis, receiving the interferon-free ABBVIE REGIMEN will be offered to participate in this study during a routine clinical visit at the participating sites.

After written Authorization (Consent) for Use/Disclosure of Data form has been obtained, patient data including demographic data, HCV disease characteristics, co-morbidities, co-medication, treatment details, and laboratory assessments as recorded in the patient's medical records (source documentation) will be documented in the electronic case report form (eCRF). Patients will be observed for the duration of the ABBVIE REGIMEN therapy and for up to 12 weeks after treatment completion. No patient identifiable information will be captured, a unique patient number will be automatically allocated by the web based eCRF system once the investigator or designee creates a new patient file.

This study is focusing on collecting real-world data. Follow-up visits, treatment, procedures and diagnostic methods will follow physicians' routine clinical practice.

12-week routine treatment regimen will include at least two observational visits (Visit 1 and EoT) plus one 30 days safety follow-up visit and one 12 weeks follow-up visit (SVR12) after the last dose of ABBVIE REGIMENT. Additional observational visits between Visit 1 and EoT can be done in case of clinical necessity and physician decision.

9.2**Product Supply**

As this is a post-marketing observational study, AbbVie is NOT involved in the product supply since the drug is being used according to the approved market label and is to be prescribed by the physician under usual, current medical practice and is clearly separated from the decision to include the patient in the study.

9.3**Setting**

For the purpose of this program participants will be recruited and observed in approximately 5-7 national and regional hospitals/outpatient services.

9.4**Program Duration**

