Enrollment will start in March 2017 and continue approximately 6 months and ABBVIE REGIMEN therapy will be administered according to physician's prescription and the local label to all enrolled subjects. All visits of the program will be organized according to routine clinical practice over 12 weeks of treatment period as well as 12 weeks follow-up period to assess the SVR12. All enrolled patients will be followed by a personal or telephone contact at 30 days after their last dose in the study.

9.5**Investigator selection criteria**

In order to assure credibility of the final results the below listed criteria will be considered during the recruitment process of physician/investigators:

- Physician licensed in infection diseases or gastroenterology;
- Physician is working at a national or regional hospitals or outpatient centers;
- Availability of patient population fulfilling the inclusion/exclusion criteria;
- Ability to appropriately conduct the observational program.

9.6**Inclusion Criteria**

ABBVIE REGIMEN will be prescribed by physicians according to the routine clinical practice. Patient can be included in the study if he/she will satisfy the following criteria:

1. Age \geq 18
2. Treatment-naïve or IFN/RBV-experienced adult male or female patients with confirmed CHC Gt1b and compensated liver cirrhosis, receiving therapy with the interferon-free ABBVIE 3D REGIMEN initiated not earlier than 2 weeks before the enrollment or the initiation is planned not later than 2 weeks after the day of enrollment in accordance to standard of care and in line with the current local label.
3. Patients must voluntarily sign and the Authorization (Consent) for Use/Disclosure of Data form prior to inclusion into the study.
4. Patient must not be participating or intending to participate in a concurrent interventional therapeutic trial.

9.7**Exclusion Criteria**

A patient will not be eligible for this PMOS if he/she fulfils the following criteria:

1. Co-administration RBV with the ABBVIE REGIMEN
2. Patients with Child Pugh B and C cirrhosis
3. Patients with a history of prior DAA therapy
4. Any other contraindications to the administration of ABBVIE REGIMEN according to the label

9.8**Description of Activities**

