9.13.4 Primary Effectiveness Endpoint

The percentage of patients achieving SVR12 (single last HCV RNA <50 IU/mL 12 weeks [i.e. at least 84 days] after the last actual dose of the ABBVIE REGIMEN) is the primary effectiveness endpoint.

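### The planned End of Data Collection (10-Dec-2017) falls about 11 weeks before the last SVR12 sample implied by the protocol's own enrolment, treatment and follow-up periods

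*Protocol*

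**What the plan says.** The Abstract (Protocol 4.0) and Section 6.0 carry the same three milestones: data collection starts on 10-Mar-2017, then "End of Data Collection: 10-Dec-2017", then the final report on 30-Mar-2018. Section 6.0 introduces them with "Major study milestones and their planned dates are as follows". Section 5.0 lists no amendments.

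The durations are given elsewhere in the protocol:

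- Section 9.4: "Enrollment will start in March 2017 and continue approximately 6 months". Visits then run "over 12 weeks of treatment period as well as 12 weeks follow-up period to assess the SVR12".
- Section 9.6: treatment may be "initiated not earlier than 2 weeks before the enrollment or the initiation is planned not later than 2 weeks after the day of enrollment".
- Section 9.1: "Patients will be observed for the duration of the ABBVIE REGIMEN therapy and for up to 12 weeks after treatment completion".
- Section 9.13.4 defines the primary endpoint as "single last HCV RNA <50 IU/mL 12 weeks [i.e. at least 84 days] after the last actual dose of the ABBVIE REGIMEN".
- Section 9.13.1: if, after the permitted imputation, an HCV RNA value "remains missing at a specific time point, then the patients will be considered as virological failure" at that time point.

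SAP section 14 places the single statistical report after data collection has ended and the database is locked. Neither document says whether the calendar milestone or the per-patient follow-up defines that end.

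**The concern.** Data collection is given 9 calendar months. Six months of enrolment followed by 24 weeks of treatment and follow-up for the last patient needs about eleven and a half. Both statements are in the current protocol and they cannot both be met.

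The quantity affected is the primary endpoint. If the milestone were applied as a cut-off, patients enrolled late would have no sample at 84 days or later. Section 9.13.1 would then count them as virological failures in the core population, which Section 9.13.3 makes the basis of the primary analysis. In the central case the last patient's 30-day safety contact would also fall after the milestone.

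**Working it through.** **Inputs**

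- Start of data collection 10-Mar-2017 and end 10-Dec-2017: Protocol 4.0 and 6.0.
- Enrolment from March 2017 (day not given) for about 6 months: 9.4.
- Treatment of 12 weeks: 9.4. With the first dose on day 1 and the last on day 84, first to last dose is 83 days.
- Primary sample at least 84 days after the last dose: 9.13.4.
- Treatment start from 14 days before to 14 days after enrolment: 9.6.

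**The plan's own figure.** From 10-Mar-2017 to 10-Dec-2017 is 275 days. Enrolment from 10 March to 10 September takes 184 of them, leaving 275 − 184 = 91 days. The last patient needs 83 + 84 = 167 days. The shortfall is 167 − 91 = 76 days, so 10-Dec-2017 is not reproduced.

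**Formula.** Earliest date of the last SVR12 sample = last enrolment + treatment-start offset + 83 + 84 days.

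| Case | Last enrolment | Offset (days) | Last SVR12 sample | Days after 10-Dec-2017 |
|---|---|---|---|---|
| Central | 10-Sep-2017 | 0 | 24-Feb-2018 | 76 (10.9 weeks) |
| Earliest, 6 months | 31-Aug-2017 | −14 | 31-Jan-2018 | 52 (7.4 weeks) |
| Latest, 6 months | 30-Sep-2017 | +14 | 30-Mar-2018 | 110 (15.7 weeks) |
| 5 months from 10 March | 10-Aug-2017 | −14 | 10-Jan-2018 | 31 (4.4 weeks) |
| 5 months from 10 March | 10-Aug-2017 | 0 | 24-Jan-2018 | 45 (6.4 weeks) |
| 5 months from 10 March | 10-Aug-2017 | +14 | 07-Feb-2018 | 59 (8.4 weeks) |

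Counting 84 days instead of 83 for treatment moves each date by one day. The 52-day figure assumes enrolment from 1 March, before the stated start of data collection. From 10 March with the −14-day offset, the 6-month gap is 76 − 14 = 62 days.

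**Working back.** 10-Dec-2017 − 167 days = 26-Jun-2017. This is the latest enrolment date that fits, 108 days (about 3.5 months) after 10 March. With the ±14-day offset it runs from 12 June to 10 July.

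**Safety contact.** Central last dose: 10-Sep-2017 + 83 days = 02-Dec-2017. Adding 30 days gives 01-Jan-2018, 22 days after the milestone.

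**Report date.** From 24-Feb-2018 to 30-Mar-2018 is 34 days. In the latest case the last sample falls on the report date itself.

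**The case against.** The strongest reply is that nothing is lost in practice. Section 6.0 calls the dates planned. Sections 9.1, 9.4 and 11.1.4 set follow-up for each patient, not by calendar. SAP 2.0 is effective 19-Mar-2018 and had to be final before database soft lock, so the database was evidently expected to be open some three months after the milestone. This stands, and it is why the point is minor.

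A second reply is that the sample is fixed at 60 patients and *approximately 6 months* is only an estimate of how long they take to recruit. This stands in part. A reader might infer from the table that no enrolment pattern can meet the date, and that would be wrong: completing enrolment by about late June 2017 would meet it. But the protocol does not plan that, and 5 months would still be too long.

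A reader might also infer that a large share of patients would lose SVR12 and that the response rate would be heavily depressed. The documents do not support a figure. It would need both a hard cut-off, which they make unlikely, and an accrual pattern, which they do not give. Safeguards also exist. The CPSFU analysis leaves out responders whose SVR12 is missing for reasons unrelated to safety or effectiveness. SAP section 9 has a separate category for missing SVR12 and repeats the frequency tables without those patients.

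Finally, the SAP's Table 4.2 window, which opens before day 84, might seem to ease the timing. That table is introduced for clinical laboratory results, and SAP 3.2 keeps the 84-day minimum for the primary endpoint.

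**Conclusion.** The milestone in 4.0 and 6.0 does not reconcile with Section 9.4 and the 84-day rule in 9.13.4. The gap is 76 days (about 11 weeks) in the central case, which assumes enrolment from 10-Mar-2017 to 10-Sep-2017, treatment starting on the day of enrolment and a full 12-week course. It is 52 to 110 days with enrolment ending between 31 August and 30 September and the ±14-day treatment start, and 31 to 59 days if enrolment takes 5 months.

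This is a minor correction. The documents do not make 10-Dec-2017 a data cut-off, and harm to the primary analysis would arise only if someone applied it as one. Nor do they show which statement is wrong, the milestone or the enrolment period. A reader might infer that the report date was derived from the faulty milestone, but no passage says how it was set. In the central case it still falls after the last sample.

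**What to change.** In Protocol 4.0 and 6.0, restate End of Data Collection as the last patient's last dose plus at least 84 days and a visit allowance, which is about late February to the end of March 2018 for the stated enrolment. Alternatively, reconcile the date with 9.4 in another way. Add one sentence saying that the planned calendar date does not truncate any patient's SVR12 or 30-day safety follow-up. Then check that 30-Mar-2018 still leaves enough time for cleaning, lock and reporting.

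The cost is an administrative edit to two lists and one added sentence, with no extra patients, visits or procedures. The downside is that the report may be later.
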